5.6 Concurrent care

Participants may continue to see their current mental health clinicians through the course of the trial in order to minimize disruption in existing treatment. Communication with the treating provider(s) will be made prior to the onset of treatment with the participant's knowledge and permission.

5.7 Payment of participants

Participants will be compensated for each assessment visit, with increasing amounts to promote retention and study completion. Participants will receive \$20 for completing the baseline assessment, \$30 for completing the post-treatment assessment, and \$50 for completing the follow-up assessment, for a total of \$100 per participant. To offset transportation costs and promote treatment retention, participants will be compensated \$10 for each tDCS clinic visit, for a total of \$100 per participant. The total compensation per participant is \$200.

6.0 Assessment of Safety and Regulatory Reporting

6.1 Data Safety and Management Plan

6.1.1 Data Management

Research data will be maintained on password protected computers, behind UM firewalls. All enrolled participants will receive participant identifiers, which will be used to code all research records for this project. Paper records with no identifying data beyond the research code are stored in locked cabinets in the PI's office. Copies of executed consent forms will be stored in separate locked cabinets. Demographic data will be entered into spreadsheets, and behavioral data will be merged into files. Password-protected electronic files separated from the research data will track consents, including the link between the research identifier and individual participants. This tracking file will be the sole link

between participant identifiers and research data. By deleting the field linking identifiers with participant names, research records can be effectively anonymized.

6.1.2 Management of withdrawals and drop-outs

Procedures for these events are described in sections 4.4.2, 4.4.3, and 4.4.4.

6.1.3 Adverse Events (AEs)

An AE is defined as any untoward occurrence in a patient or clinical investigation participant administered an intervention regardless of its causal relationship to the study treatment. An AE can therefore be any unfavorable and unintended sign (including an abnormal laboratory finding), symptom, or disease temporally associated with the use of the intervention. The occurrence of an AE may come to the attention of study personnel during study visits and interviews of a study participant presenting for medical care, or upon review by a study monitor. At each treatment session participants will be questioned about putative AEs. Information to be collected includes event description, time of onset, clinician's assessment of severity (mild, moderate, or severe), relationship to study product (assessed by the study clinician, [name]), expected versus unexpected, local versus systemic, and time of resolution/stabilization of the event. All AEs occurring while on study will be documented appropriately regardless of relationship. All AEs will be followed to adequate resolution. Adverse event reporting will occur on the standard IRBMED timetable.

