3.0 Study Design

3.1 Overview of Experimental Design

Aim 1 (feasibility and acceptability) will include a randomized crossover design, where all 12 participants will receive both the combined intervention (active tDCS plus BrainHQ computerized cognitive training), and computerized cognitive training alone, with starting condition randomly determined. Aim 2 (efficacy) will be a randomized, controlled trial, where half of the participants (n=15) will be randomized to receive active transcranial direct current stimulation (tDCS) plus BrainHQ computerized cognitive training, and half (n=15) will receive sham tDCS plus BrainHQ computerized cognitive training (Table 1). Participants will attend 10 treatment sessions in the clinic. If able to attend daily, participants will complete these sessions in 2 weeks; to allow for unanticipated absences or difficulty with attendance, up to 4 weeks will be permitted for completion. Following completion of these 10 treatment sessions, participants will return after one month of no study contact to complete a follow-up assessment.

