5.2.3 Stopping Rules

In the event that a participant reports discomfort during the tDCS procedure, stimulation will be paused and additional saline/gel will be added to improve the contact, or the current will be incrementally reduced. The session will be discontinued if the patient reports continued discomfort. Immediately after each stimulation session ends, participants will complete a tDCS side effects questionnaire. A study team member will review the responses and will immediately consult the PI if a participant reports a moderate-severe rating for any of the side effects. Those participants, if any, will be given the option of withdrawing from the study. The PI will also withdraw participants if the nature of the side effect is unusual (i.e., not listed as a common side effect) or concerning (e.g., significant acute mood change). Clinically trained study staff will monitor participants closely for mood changes and/or any emergence of suicidal ideation throughout the duration of participation. Participants will be withdrawn in the event of significant symptomatic worsening, including:

1. Current mania: YMRS change of ≥ 7 points at mid-point assessment or clinical observation indicating current mania
2. Worsening of depressive symptoms: 25% increase (i.e., greater severity) in HAM-D total score at mid-point assessment
3. Worsening of psychosis: 25% increase (i.e., greater severity) in PANSS positive total score at mid-point assessment
4. Suicide risk evaluated by a clinician to be high and imminent (e.g., current suicide plan and intent)

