6.1.4 Serious Adverse Events (SAEs)

An SAE is defined as an AE that meets one of the following conditions:

Death during the period of protocol-defined surveillance

Life-threatening event (i.e., a participant at immediate risk of death at the time of the event)

An event requiring inpatient hospitalization or prolongation of existing hospitalization during the period of protocol defined surveillance

Results in congenital anomaly or birth defect

Results in a persistent or significant disability/incapacity

Any other important medical event that may not result in death, be life threatening, or require hospitalization, may be considered a serious adverse experience when, based upon appropriate medical judgment, the event may jeopardize the participant and may require medical or surgical intervention to prevent one of the outcomes listed above. Examples of such medical events include allergic bronchospasm requiring intensive treatment in an emergency room or at home, blood dyscrasias or convulsions that do not result in inpatient hospitalization, or the development of drug dependency or drug abuse/overdose or cancer.

All SAEs will be:

- Followed through resolution by a study clinician
- Reviewed and evaluated by a study clinician
- Reported to Soterix, the company supplying the tDCS unit to the investigators

The study will comply with IRB and FDA reporting requirements and guidelines for SAEs.

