Active tDCS may have no benefit. The general consensus is that tDCS is extremely safe. In a meta-analysis of over 200 tDCS studies conducted from 1998 to 2010, 56% of studies mentioned adverse events¹². The events were generally minor, including itching, tingling, headache, burning sensation and discomfort limited to the scalp site where the tDCS electrodes were applied. To date, there have been no reports of seizures or other severe events induced by tDCS^{12,13}. Importantly this is the case in both healthy volunteers and in different populations of patients, including patients with disorders where there might be an increased risk of seizures (e.g. Alzheimer's disease, recent stroke, epilepsy). For this study, an intensity not to exceed 2 mA will be used, for a duration of 20 minutes; little of this current actually reaches the brain since it must first pass through the scalp (skin, fat, etc), skull, and cerebrospinal fluid. Few, if any, side effects are reported with these parameters and those that are reported are mild in nature (e.g., tingling, itching, burning sensation; Nitsche & Paulus, 2011). Nevertheless, side effects of tDCS are possible. The most common side effects associated with tDCS based on the available scientific data are:

1) Sensations under the electrode: these sensations usually stop shortly after tDCS begins but can sometimes continue throughout and for a brief period after tDCS.

- Mild tingling
- Light itching
- Slight burning sensation
- Discomfort

2) Reported effects that occur only DURING tDCS:

- Visual sensation during switching on and off the stimulation

3) Other effects that can occur both DURING and AFTER tDCS:

- Fatigue
- Skin redness
- Headache
- Changes in concentration, memory, or other cognitive abilities. This is partially what the proposed study will be testing.

Additionally, the following rare side effects have been described in previous studies that used tDCS:

- 1) Nausea
- 2) Nervousness
- 3) It is also possible that the electric current can cause a burn on the skin. This is unlikely because we are using a smaller dose than what is known to cause burns and because we use saline or gel to reduce electrical resistance that leads to burns.
- 4) A shock-like sensation at the initiation of tDCS was reported in one participant.

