- 5) Changes in the activity of the prefrontal region (front of the head) have the potential to induce sudden changes in mood. Hypomania has been reported in a few patients receiving tDCS for bipolar disorder and depression.

To minimize risk: Clinically trained study staff will monitor participants closely for changes in mood or psychosis and/or any emergence of suicidal ideation throughout the duration of participation. In the event of significant symptomatic worsening (as detailed in 5.2.3 *Stopping Rules*), the PI will be promptly notified, and plans will be formulated for additional emergency evaluation at the psychiatric emergency room (University of Michigan Psychiatric Emergency Services), if appropriate. Similarly, if the evaluation of a

participant uncovers suicidal plans or intentions, the same procedures for emergency evaluation will be followed.

Importantly, the majority of the above side effects have also been reported in association with sham (fake) tDCS, with similar rates. The table below comes from a recent review of tDCS safety and shows the percentage of studies reporting these common sensations¹². These data suggest that other factors may cause these sensations, such as participant expectations or the pressure of head straps or caps.

Sensation	Real tDCS	Sham tDCS
Itching	39.3%	32.9%
Tingling	22.2%	18.3%
Headache	14.8%	16.2%
Burning	8.7%	10.0%
Discomfort	10.4%	13.4%

To minimize risk: The researchers will ensure that participants are fully informed of the risks during the informed consent process, and will adhere to best-practice standards for tDCS procedures.

Due to the investigational nature of the study, there may be risks, discomforts, or side effects that are not yet known.

For women of child-bearing potential: It is unknown if tDCS can pose a risk to fetuses or if it decreases milk production in women who are lactating.

To minimize risk: Participants are asked during their screening whether they are pregnant or are trying to become pregnant, or are currently lactating, and are not enrolled in the study if they are. Urine pregnancy screening can be made available to potential participants as requested. Sexually active women of child-bearing potential will be asked to use a reliable birth control method for the duration of this study.

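### No adverse-event question is scheduled after the last treatment session, so in Aim 2 later events depend on passive reporting

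*Combined protocol and SAP*

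**What the plan says.** **When AEs are asked about.** Section 6.1.3: "At each treatment session participants will be questioned about putative AEs". No other time point is given for a question. The same section allows for passive detection ("The occurrence of an AE may come to the attention of study personnel during study visits and interviews of a study participant") and makes a general commitment: "All AEs occurring while on study will be documented appropriately regardless of relationship".

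**Side-effects form.** Section 5.2.3: "Immediately after each stimulation session ends, participants will complete a tDCS side effects questionnaire". It is not scheduled at any other time.

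**Visits after treatment.** Section 5.4 and the 5.5 table list HAM-D, YMRS, PANSS, three MCCB tests, Trails B and SLOF at post-treatment and at follow-up. Neither contains an AE item.

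**The interval.** For Aim 2, section 3.1 says that after the 10 sessions "participants will return after one month of no study contact to complete a follow-up assessment". The 3.4 schematic marks Weeks 5-8 as having no contact.

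**Expected effects.** Section 11.3.3 has a group headed "Other effects that can occur both DURING and AFTER tDCS", which includes fatigue, skin redness and headache. It lists skin burn as possible and adds: "Hypomania has been reported in a few patients receiving tDCS for bipolar disorder and depression".

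**Serious events.** In 6.1.4 the death criterion reads "Death during the period of protocol-defined surveillance", and the hospitalization criterion carries the same limit. No section gives that period a start or an end.

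**The concern.** The protocol expects some effects to appear after stimulation and undertakes to record all AEs on study, but it stops asking once the sessions stop. An event that nobody asks about is reported less reliably than one that is asked about. A low count of late events would then reflect partly what happened and partly the lack of a question, and the data could not separate the two.

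This matters most for events that the repeated scales are not built to record: a skin burn, persistent headache, an emergency visit, an admission, or a mood episode that began and resolved between two visits. The study is described as a first step toward a larger trial, whose planners would want a usable description of the weeks after stimulation.

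The undefined surveillance period is a smaller matter. It leaves staff without a written rule for whether a death or admission in the follow-up month meets those two criteria.

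**Working it through.** The plan states no figure on this point. The check compares sections and does simple arithmetic on the schedule.

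**Step 1. What each contact collects in Aim 2**

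| Contact | AE question (6.1.3) | Side-effects form (5.2.3) | HAM-D, YMRS, PANSS (5.4, 5.5) |
|---|---|---|---|
| Sessions 1 to 10 | yes | yes | not listed |
| Post-treatment visit | not scheduled | not scheduled | yes |
| Month without contact | none | none | none |
| Follow-up visit | not scheduled | not scheduled | yes |

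The early-termination visit (5.2.4) repeats the final visit's assessments, so it adds no AE question.

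**Step 2. Which exposures are affected.** A delayed effect of sessions 1 to 9 can be reported at the next session. Effects present when session 10 ends are caught by the form completed then. What remains is delayed effects of session 10 (1 of 10 exposures), plus any event that begins in the weeks after it.

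**Step 3. How long the interval is.** Inputs: sessions take 2 weeks with daily attendance and at most 4 (3.1); one month is counted as 4 weeks, in line with Weeks 5-8 in 3.4.

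Share of time from first session to follow-up with no scheduled AE question = interval / (treatment + interval):
- sessions over 4 weeks: 4 / (4 + 4) = 50%
- sessions over 2 weeks: 4 / (2 + 4) = 67%

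Section 6.2 allows 10 days either side of the assessment, weekends excluded. Ten weekdays are about 2 calendar weeks, so the time from last session to follow-up can reach about 4 + 2 = 6 weeks.

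**Step 4. Whether the visits have room.** Times from the 5.5 table, reading 15-30 minutes as the total for the three clinical scales: (15 to 30) + 30 + 5 + 10 = 60 to 75 minutes, against a stated maximum of 1.5 hours (90 minutes). That reading fits the baseline column: 60 + 30 + 5 + 5 + 30 + 5 + 10 = 145 minutes, within the stated 2.5 hours (150 minutes). At least 90 - 75 = 15 minutes remain at each later visit.

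**Step 5. Serious-event criteria.** Of the six conditions in 6.1.4, two (death and hospitalization) depend on the undefined period. The other four (life-threatening event, congenital anomaly, disability, other important medical event) do not.

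**The case against.** The strongest reply is that the protocol does have safety contact after session 10. HAM-D, YMRS and PANSS are done at both later visits. Section 6.2 calls them safety-related and makes a missed or out-of-window one a reportable deviation. Section 6.1.3 foresees AEs coming to light at visits, and 6.1.5 has unanticipated problems recorded throughout.

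Much of this stands, and it rules out several stronger readings that a reader might infer:
- *Late events are invisible.* Not supported: passive capture at visits is provided for. What is missing is a scheduled question.
- *Delayed mood switches would be missed.* Not supported in general: YMRS, HAM-D and PANSS are repeated at both visits. Only an episode that resolved in between could escape them.
- *An admission in the follow-up month is not a serious event.* This requires equating surveillance with the days on which AEs are asked about. Time on study is the more natural reading, given the 6.1.3 commitment and the 2-month participation in the protocol summary.
- *Sites could classify the same event differently.* The trial has one site.
- *A safety objective is undermined.* The stated aims are feasibility, acceptability and initial efficacy. Safety is not a named aim or outcome.
- *Half of Aim 1 Group A's time is also uncovered.* The documents do not say whether training-only work counts as a treatment session for AE questioning, so no figure can be given.

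The reply does not close the gap itself. Passive detection is not a question and has no recall period. The scales do not record burns, headaches, emergency visits or admissions. Unanticipated problems must be unexpected, related and suggestive of greater risk, so effects already described in 11.3.3 would usually not qualify.

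**Conclusion.** The point holds as a gap in ascertainment, not in stated intent. In Aim 2, AEs that begin after session 10 have no scheduled question for about 4 weeks. That is 50% to 67% of the time from first session to follow-up, and the interval can reach about 6 weeks at the late edge of the visit window. These shares measure calendar time without a question, not a proportion of events lost; the documents give no basis for estimating the latter. They rest on a month of 4 weeks and on sessions completed in 2 to 4 weeks.

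The likely loss is concentrated in somatic events, emergency visits, admissions and resolved episodes. Mood and psychosis worsening that is still present at a visit is partly covered. The surveillance period is a missing detail with a natural reading, so it needs a clarifying sentence only. The efficacy analysis is unaffected. The change is worth making because it is cheap and improves the safety record.

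**What to change.** 1. **Section 6.1.3.** Extend the questioning, for example: *Participants will be asked about AEs at each treatment session and, at every assessment visit after treatment starts (Aim 1 mid-point and post-treatment; Aim 2 post-treatment and follow-up), about AEs since the last contact, including emergency visits and hospital admissions.*
2. **Section 5.4 and the 5.5 table.** Add a matching AE row at those visits. The early-termination visit then inherits it through 5.2.4. The post-stimulation side-effects form need not be repeated at follow-up.
3. **Section 6.1.4 (secondary).** State that the surveillance period in the death and hospitalization criteria is the time on study, through the final assessment visit.

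No new visit is needed. The cost is protocol wording, one short form, an assumed few minutes per visit within the 15 or more minutes available, and slightly more events to document.

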6.1.4 Serious Adverse Events (SAEs)

An SAE is defined as an AE that meets one of the following conditions:

Death during the period of protocol-defined surveillance

Life-threatening event (i.e., a participant at immediate risk of death at the time of the event)

An event requiring inpatient hospitalization or prolongation of existing hospitalization during the period of protocol defined surveillance

Results in congenital anomaly or birth defect

Results in a persistent or significant disability/incapacity

Any other important medical event that may not result in death, be life threatening, or require hospitalization, may be considered a serious adverse experience when, based upon appropriate medical judgment, the event may jeopardize the participant and may require medical or surgical intervention to prevent one of the outcomes listed above. Examples of such medical events include allergic bronchospasm requiring intensive treatment in an emergency room or at home, blood dyscrasias or convulsions that do not result in inpatient hospitalization, or the development of drug dependency or drug abuse/overdose or cancer.

All SAEs will be:

- Followed through resolution by a study clinician
- Reviewed and evaluated by a study clinician
- Reported to Soterix, the company supplying the tDCS unit to the investigators

The study will comply with IRB and FDA reporting requirements and guidelines for SAEs.

6.1.5 Unanticipated Problems

The Office for Human Research Protections (OHRP) considers unanticipated problems involving risks to participants or others to include, in general, any incident, experience, or outcome that meets all of the following criteria:

- Unexpected (in terms of nature, severity, or frequency) given (a) the research procedures that are described in the protocol-related documents, such as the IRB-approved research protocol and informed consent document; and (b) the characteristics of the participant population being studied;
- Related or possibly related to participation in the research (in the guidance document, possibly related means there is a reasonable possibility that the incident, experience, or outcome may have been caused by the procedures involved in the research); and suggests that the research places participants or others at a greater risk of harm (including

- physical, psychological, economic, or social harm) than was previously known or recognized.
- An incident, experience, or outcome that meets the three criteria above generally will warrant consideration of substantive changes in order to protect the safety, welfare, or rights of participants or others.

Unanticipated problems will be recorded and reported throughout the study.

6.2 Event Windows, Missed Assessments/Sessions and Protocol Deviation Reporting

For the post-treatment and follow-up assessments, a window of \pm 10 days will be permitted (not including weekends). Any safety-related assessments (HAM-D, YMRS, PANSS, C-SSRS) or primary outcome measure (MCCB working memory) which are missed or obtained outside the window will be reported to the IRB as a protocol deviation. However, for the other assessments, missing or late assessments will not be reported as protocol deviations unless they constitute > 10% of the total assessments. In order to accommodate inevitable scheduling conflicts, holidays, etc., participants will be allowed to complete the 10 tDCS sessions within 4 weeks. Participants who do not complete all 10 tDCS sessions or all 10 hours of cognitive training will be retained in the study and their outcome data will be compared to those participants who completed the full course of treatment. These allowances should affect neither the scientific integrity nor the safety monitoring provisions of the protocol.

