4.2 Exclusion Criteria

(1) history of neurological illness or brain injury (e.g., stroke), (2) history of loss of consciousness > 20 minutes, (3) diagnosed intellectual disability, (4) current (i.e., past 30 days) substance use disorder, (5) current mania (YMRS \geq 10) or moderate depression (HAM-D \geq 17) or severe psychosis (PANSS positive symptom total \geq 35), (6) serious suicidal ideation/behavior (endorse questions 4 or 5 or suicide behaviors within the past 3 months, according to the C-SSRS), (7) pregnant or trying to become pregnant, or currently lactating, (8) presence of metal (except titanium) or electrical implants in the brain or skull (e.g., surgical clips, deep brain stimulator, cochlear implants, splinters/fragments, skull plate), (9) presence of implanted medical devices elsewhere in the body (e.g., cardiac pacemaker or medical pump).

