5.1.2 Initial Assessments

This session will continue with completion of a brief demographic questionnaire and clinical measures to confirm eligibility and characterize current symptoms. These include:

1. Mini-International Neuropsychiatric Interview (MINI), a short structured diagnostic interview for DSM-IV and ICD-10 psychiatric disorders
2. Hamilton Depression Rating Scale (HAM-D)
3. Young Mania Rating Scale (YMRS)
4. Positive and Negative Syndrome Scale (PANSS)
5. Columbia Suicide Severity Rating Scale (C-SSRS)

Note. To allow for maximal appropriate distancing owing to the ongoing COVID-19 pandemic, these interview-based clinical measures may be completed virtually while the participant is physically in the building and the clinician is in a remote location, via a secure and approved telehealth platform (Zoom for Health). Because the participant will be in the clinic with another study staff member (who will be administering the informed consent and the portion of the assessment that requires manipulation of materials), there are no anticipated changes to safety or risk-assessment protocols. Any safety concerns will be immediately communicated between the study clinician and research assistant, and appropriate action will be taken (see section 5.5.1).

Neuropsychological and functional measures will also be administered to characterize current neurocognitive functioning. These include:

1. Wide Range Achievement Test, reading subtest (WRAT-4)
2. MCCB: Trails A, letter-number span, spatial span
3. Trails B
4. Specific Levels of Functioning (SLOF) clinician-rated questionnaire

This screening and initial assessment visit is expected to last up to 2.5 hours.

5.2 tDCS Treatment visits

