5.2.4 Early Termination Assessments

If early termination occurs and, if the participant is willing and able, all of the outcomes and safety assessments noted above for the final experimental visit will be performed.

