5.4 Subsequent assessment visits (post-treatment and follow-up)

Participants will complete follow-up assessments at the conclusion of treatment (post-treatment) and at one-month follow-up. Measures will include:

1. Hamilton Depression Rating Scale (HAM-D)
2. Young Mania Rating Scale (YMRS)
3. Positive and Negative Syndrome Scale (PANSS)
4. MCCB: Trails A, letter-number span, spatial span
5. Trails B
6. Specific Levels of Functioning (SLOF) clinician-rated questionnaire

These visits are expected to last up to 1.5 hours.

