5.5 Assessments

Participants will complete assessments at three time points: baseline (pre-treatment), post-treatment, and follow-up.

Assessment schedule and administration time requirements.

	Baseline	Post-treatment	Follow-up	Administration time (mins)
Clinical measures				
MINI diagnostic interview	x			60
HAM-D, YMRS, PANSS	x	x	x	15-30
C-SSRS	x			5
Neuropsychological measures				
WRAT reading	x			5
MCCB (Trails A*; letter-number span; spatial span)	x	x	x	30
Trails B*	x	x	x	5
Functional measures				
SLOF	x	x	x	10
Total estimated time	≤ 2.5 hours	≤ 1.5 hours	≤ 1.5 hours	

*Trails A and B will be administered as non-working memory neurocognitive comparison measures

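### Section 6.2 makes a missed or late C-SSRS reportable under a window set for the two later visits, but the schedule gives the C-SSRS at baseline only and never after stimulation

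*Combined protocol and SAP*

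**What the plan says.** Section 6.2 allows 10 days either side, weekends not counted, for the post-treatment and follow-up assessments. The next sentence makes reportable to the IRB "Any safety-related assessments (HAM-D, YMRS, PANSS, C-SSRS) or primary outcome measure (MCCB working memory) which are missed or obtained outside the window". The other time limit in the paragraph, 4 weeks, applies to the ten tDCS sessions and not to assessments.

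The schedule is in three places:

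- Section 5.1.2 lists the C-SSRS as the fifth clinical measure at the initial visit.
- Section 5.4 states "Participants will complete follow-up assessments at the conclusion of treatment (post-treatment) and at one-month follow-up" and lists six measures: HAM-D, YMRS, PANSS, the MCCB subtests, Trails B and SLOF. The C-SSRS is not among them.
- Section 5.5 states "Participants will complete assessments at three time points: baseline (pre-treatment), post-treatment, and follow-up". Its table marks the HAM-D, YMRS and PANSS at all three visits and the C-SSRS at baseline alone, with 5 minutes of administration time.

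At entry, 4.2 excludes people with "serious suicidal ideation/behavior (endorse questions 4 or 5 or suicide behaviors within the past 3 months, according to the C-SSRS". The preceding criterion in 4.2 sets thresholds on the YMRS, HAM-D and PANSS.

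During the study, 5.2.3 withdraws a participant for "Suicide risk evaluated by a clinician to be high and imminent (e.g., current suicide plan and intent". For early termination, 5.2.4 says that, for willing and able participants, "all of the outcomes and safety assessments noted above for the final experimental visit will be performed".

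**The concern.** There are two separate points, and the second does not follow from the first.

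The first is a mismatch. A deviation rule tied to a window for two visits names a scale that is not scheduled at either of them. Anyone auditing the later visits against 6.2 would look for a C-SSRS that 5.4 and 5.5 never ask for.

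The second is a gap that comes from 5.4 and 5.5 alone. The trial uses four symptom scales to decide who may enter, then re-rates three of them after stimulation. The one left out is the suicidality scale. Section 11.3.3 names sudden mood change as a possible effect of altering prefrontal activity and promises monitoring for emerging suicidal ideation, but no section schedules a rating on the entry scale once stimulation has started. Suicidal behavior could still be recorded as an adverse event. A structured rating of ideation on C-SSRS questions 4 and 5, the ideation part of the entry rule, would not be available.

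**Working it through.** The check is mainly a comparison of sections. The plan gives no figure on this point to reproduce.

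**Step 1. Count scheduled administrations (5.5 table, checked against 5.1.2 and 5.4).**

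| Scale named in 6.2 | Entry threshold in 4.2 | All visits | Visits after stimulation |
|---|---|---|---|
| HAM-D | yes | 3 of 3 | 2 of 2 |
| YMRS | yes | 3 of 3 | 2 of 2 |
| PANSS | yes | 3 of 3 | 2 of 2 |
| C-SSRS | yes | 1 of 3 | 0 of 2 |

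The numbered list in 5.4 agrees with the table, so the blank cells are not an artefact of reading the PDF.

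**Step 2. Apply the 6.2 rule to a baseline-only scale.** The rule has two limbs. A baseline C-SSRS can be missed, so the first limb can apply. It cannot be obtained outside the window, because 6.2 sets no window for baseline. The second limb therefore has nothing to act on for this scale.

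**Step 3. Check early termination.** Section 5.2.4 points to the assessments of the final visit. If that means the 5.4 battery, which is an inference from its wording, the C-SSRS is absent there too.

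**Step 4. Check whether an added rating fits the visit.** Listed minutes at each later visit, from the 5.5 table:

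- Now: (15 to 30 for HAM-D, YMRS and PANSS) + 30 (MCCB) + 5 (Trails B) + 10 (SLOF) = 60 to 75.
- With the C-SSRS: 60 + 5 = 65, to 75 + 5 = 80.
- Slack against 90 minutes: 90 − 80 = 10, to 90 − 65 = 25.

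This reads the 15 to 30 minutes as the total for the three scales. The baseline column supports that: 60 + (15 to 30) + 5 + 5 + 30 + 5 + 10 = 130 to 145 minutes, within the stated 150. Taken per scale, baseline would be 160 to 205 minutes and would break the limit. The treatment guess that 4.4.1 places at the post-treatment visit has no listed time, so the slack there is slightly smaller.

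**Step 5. Total added time.** Aim 2: 30 completers × 2 visits × 5 minutes = 300 minutes. If the change also covers the Aim 1 mid-point and post-treatment visits, assuming the same battery: 12 × 2 × 5 = 120 more, for 420 minutes in all.

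**The case against.** The strongest reply is that the schedule is clear. Sections 5.1.2, 5.4 and 5.5 all say baseline only, and 6.2 is a reporting rule, not a schedule. Its heading also covers missed assessments and sessions, so it may simply name instruments, with a missed baseline C-SSRS as the reportable case. That reading is possible. It fits a sentence about a later-visit window poorly, but it rules out two inferences a reader might draw: that staff cannot tell whether the scale is due, and that each later visit without a C-SSRS is a deviation. Three consistent schedule entries outweigh one loosely worded rule.

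A second reply is that suicidality is well covered. Much of this stands:

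- Clinically trained staff monitor for suicidal ideation throughout (5.2.3, 11.3.3).
- The HAM-D is repeated, and 5.5.1 names it as a source for suicidal thoughts.
- A side-effects questionnaire follows every session, with immediate PI consultation for moderate to severe ratings and PI withdrawal for acute mood change (5.2.3).
- On adverse events, 6.1.3 states "At each treatment session participants will be questioned about putative AEs", and 6.1.4 covers serious events.
- Sections 4.4.2 and 5.2.3 provide for withdrawal, and 11.3.3 for emergency evaluation.

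A reader might infer that suicidality goes unmonitored after stimulation. These provisions show that it does not.

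Third, the suicide withdrawal rule rests on clinician judgement, so an added C-SSRS would not by itself change a withdrawal decision. Ratings at post-treatment and a month later would also not catch acute effects around a session. The mood change that 11.3.3 illustrates is hypomania, which the YMRS measures at all three visits. All of this is fair and limits the weight of the point. It does not remove the mismatch in 6.2 or supply a later rating on the entry scale.

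**Conclusion.** The point holds and is minor. The deviation rule in 6.2 and the visit schedule do not match for one of the four named safety scales. That scale is the only one of the four with an entry threshold that is not repeated after stimulation. The loss is one scheduled, structured suicidality rating at each of two visits, and not the monitoring of suicidality as such.

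The documents give no rate of suicidal ideation and do not say that tDCS causes it, so the number of participants affected cannot be stated. Sample size and the efficacy analysis are unaffected. The early-termination part assumes that 5.2.4 means the 5.4 battery.

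**What to change.** Preferred: add the C-SSRS to the list in 5.4 and mark it at post-treatment and follow-up in the 5.5 table. Section 6.2 then works as written, and so does 5.2.4 if it uses the final-visit battery. As part of the same change, make 5.5.1 apply to *any potential or enrolled participant*. It is now worded for potential participants only, so read literally it would not require a risk assessment after a concerning rating at a later visit.

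Cost: about 5 minutes per visit, or 5 hours over Aim 2 (7 hours if Aim 1 is included), with no new instrument and no new visit. It needs one IRB amendment. Staff time for any risk assessment that follows cannot be costed from the documents.

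Minimum, if a baseline-only C-SSRS is intended: write *C-SSRS (baseline only)* in 6.2. That removes the mismatch at no visit cost but leaves no rating on the entry scale after stimulation.
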